5.2.2.5. ROC analysis (dose characterization)

This analysis is exploratory and complementary to traditional data analysis methods comparing post-vaccination immune responses among vaccine groups and will be performed on the PPS only if deemed necessary.

If immune response between active vaccination groups can't be differentiated using traditional approach, additional analyses using a generalized ROC (Receiver Operating Characteristics) method [Yu, 2018] will be performed for both RSV-A neutralizing antibody titers and RSVPreF3 IgG specific antibody concentrations at Day 31 and Delivery, and other timepoints if needed.

Two ROC Methods will be explored:

- ROC-P (ROC of post-dose levels) method: Post-vaccination antibody levels from 2 RSV vaccine groups (RSV MAT 60 and RSV MAT 120) will be pooled and used as a reference distribution.
- ROC-B (ROC relative to baseline) method: Overall pre-vaccination antibody levels from 2 RSV groups (RSV MAT 60 and RSV MAT 120) will be used as a reference distribution.

Different percentile (0% to 100%) thresholds from the reference distribution will be obtained. The percentage of subjects with post-vaccination antibody level higher than or equal to the percentile thresholds from the reference distribution will then be calculated for each vaccine group.

A figure will be provided showing the ROC curve with x-axis the percentile of the reference distribution and y-axis the percentage of subjects in each vaccine group with post-vaccination antibody levels higher than or equal to the percentile threshold of the reference distribution.

A summary table will be provided on the thresholds of e.g. 25%, 50% and 75% percentiles of the reference distribution and the percentage of subjects in each vaccine group with post-vaccination antibody level higher than or equal to these percentile thresholds.

CONFIDENTIAL209544 (RSV MAT-004)
Statistical Analysis Plan Amendment 3**5.3. Analysis of safety and reactogenicity****5.3.1. Analysis of safety and reactogenicity planned in the protocol**

Safety analyses in **maternal subjects** will include summaries by study group and age category (18 - < 35 years of age; ≥ 35 years of age; overall) of hematology and biochemistry results by grade and per time point, solicited administration site and systemic events, unsolicited AEs, MAEs, SAEs, MA-RTIs, RSV-associated MA-RTIs, AEs leading to study withdrawal, pregnancy outcomes and pregnancy related AESIs.

Safety analyses in **infant subjects** will include summaries by study group and gestational age at birth (> 37 weeks or ≤ 37 weeks) of neonatal AESIs, MAEs, SAEs, AEs leading to study withdrawal, and the occurrence of RSV-associated RTIs, LRTIs, severe LRTIs, very severe LRTIs and RSV-associated hospitalizations.

All safety analyses will be performed on the Solicited Safety or Exposed sets.

	Primary Safety Endpoints	Statistical Analysis Methods
Maternal subjects	Occurrence of Solicited administration site and systemic events that occur during a 7-day follow-up period after vaccination (i.e. the day of vaccination and 6 subsequent days).	
The number and percentage with exact 95% CI of maternal subjects reporting each Solicited administration site event (any grade, each grade,) and solicited systemic event (any, each grade) during the 7-day (days 1 to 7) follow-up period after vaccination will be tabulated by maximum intensity per subject for each study vaccine group.
 
For fever during the 7-day follow-up period after vaccination, the number and percentage of maternal subjects reporting any fever (i.e., temperature ≥ 38 °C) and fever by half degree (°C) cumulative increments, any Grade 3 fevers, will be reported. In addition, the prevalence of any and Grade 3 fever will be presented graphically over time after vaccination.
 
The number and percentage of maternal subjects with at least one administration site AE (solicited and unsolicited), with at least one systemic AE (solicited and unsolicited) and with any AE during the 7-day follow-up period after vaccination will be tabulated with exact 95% confidence interval (CI) by group. The same computations will be done for Grade 3 solicited and unsolicited AEs, for any AEs considered related to vaccination, for any Grade 3 AEs considered related to vaccination and for any AEs resulting in a medically attended visit (i.e., MAEs).

	Occurrence of any protocol-specified hematological or biochemical laboratory abnormality at baseline (up to 15 days before vaccination) and Day 8 (Visit 2)	The number and percentage of subjects with hematology and biochemistry results outside central laboratory normal ranges will be tabulated to show Day 8 versus baseline. The maximum grading as described in [Sheffield, 2013] and in the SPM from Screening up to Day 8 will also be tabulated.

CONFIDENTIAL209544 (RSV MAT-004)
Statistical Analysis Plan Amendment 3

	Primary Safety Endpoints	Statistical Analysis Methods
	Occurrence of unsolicited AEs that occur during a 30-day follow-up period after vaccination (i.e. the day of vaccination and 29 subsequent days).	
The number and percentage of maternal subjects with unsolicited symptoms within 30 days after vaccination with exact 95% CIs will be tabulated by group and by Medical Dictionary for Regulatory Activities (MedDRA) preferred term.
 
Similar tabulations will be done for Grade 3 unsolicited symptoms, for any causally related unsolicited symptoms, for Grade 3 related unsolicited symptoms and for MAEs.
 
The number and percentage of maternal subjects with at least one administration site AE (solicited and unsolicited), with at least one systemic AE (solicited and unsolicited) and with any AE during the 30-day follow-up period after vaccination will be tabulated with exact 95% confidence interval (CI) by group. The same computations will be done for Grade 3 solicited and unsolicited AEs, for any AEs considered related to vaccination, for any Grade 3 AEs considered related to vaccination and for MAEs.

	Occurrence of serious adverse events (SAEs), AEs leading to study withdrawal, and medically attended AEs from Visit 1 (Day 1) up to 6 weeks after delivery (Day 43 post-delivery, Visit 6).	
The number and percentage of maternal subjects with
 
 - at least one SAE; - at least one MAE from Visit 1 (Day 1) up to 6 weeks after delivery with exact 95% CIs will be tabulated by group and by Medical Dictionary for Regulatory Activities (MedDRA) preferred term. 
By-subject listings of SAEs, AEs leading to study withdrawal, and MAEs will be prepared (but will not be released until the final, unblinded analysis has been completed).

	Pregnancy outcomes from Day 1 (Visit 1) up to 6 weeks after delivery (Day 43 post-delivery, Visit 6). Outcomes are listed in Section 2.	
The number and percentage of maternal subjects with each pregnancy outcome will be tabulated with its exact 95% CI by group.
 
By subject listings of adverse pregnancy outcomes will be prepared but will not be released until the final, unblinded analysis has been completed.

	Pregnancy-related AESIs from Day 1 (Visit 1) up to 6 weeks after delivery (Day 43 post delivery; Visit 6). These events are listed in Section 2.	
The number and percentage of maternal subjects with each pregnancy-related AESI will be tabulated with its exact 95% CI by group.
 
By subject listings of pregnancy-related AESIs will be prepared but will not be released until the final, unblinded analysis has been completed.

CONFIDENTIAL209544 (RSV MAT-004)
Statistical Analysis Plan Amendment 3

Primary Safety Endpoints		Statistical Analysis Methods
Infant subjects	
The occurrence of neonatal AESIs (reported up to 6 weeks after birth). These events are listed in Section 2.
 
Occurrence of SAEs, AEs leading to study withdrawal and medically attended AEs from birth up to 6 weeks after birth.
	
The number and percentage of infant subjects with each neonatal AESI will be tabulated with its exact 95% CI by group.
 
By-subject listings of neonatal AESIs will be prepared, but will not be released until the final, unblinded analysis has been completed.
 
The number and percentage of infant subjects with
 
 - at least one SAE; - at least one MAE 
from Visit 1 (Day 1) up to 6 weeks after delivery with exact 95% CIs will be tabulated by group and by Medical Dictionary for Regulatory Activities (MedDRA) preferred term.
 
By-subject listings of SAEs, AEs leading to study withdrawal, and MAEs will be prepared (but will not be released until the final, unblinded analysis has been completed).

Secondary Safety Endpoints		Statistical Analysis Methods
Maternal subjects	
From Day 1 (Visit 1) through 6 months after delivery (Visit 8), occurrences of SAEs, MAEs and AEs leading to study withdrawal.
 
Occurrence of RSV-associated medically attended RTIs (RSV-MA-RTIs) up to 6 months post-delivery (Visit 8)
	
The number and percentage of maternal subjects with at least one SAE, MAE from Day 1 up to 6 months after delivery with exact 95% CIs will be tabulated by group and by Medical Dictionary for Regulatory Activities (MedDRA) preferred term.
 
By-subject listings of SAEs, AEs leading to study withdrawal and MAEs will be prepared (but will not be released until the final, unblinded, analysis has been completed).
 
The number and proportion of subjects with at least one RSV-associated MA- RTI (with 95 % CI) will be calculated and tabulated.

Infant subjects	
From birth through 6 months (Visit 4-NB) after birth, occurrences of SAEs, AEs leading to study withdrawal, and medically attended AEs
 
From birth through 1 year (Visit 5-NB) after birth, occurrences of SAEs, AEs leading to study withdrawal, and MAEs
	
For each category:
 
 - SAE, - MAEs 
The number and proportion of infant subjects who experienced at least one event from birth up to 6 months after birth and the number and proportion of infant subjects who experienced at least one event from birth up to 1 year after birth will be tabulated with 95% CI by group.
 
By-subject listings of SAEs, AEs leading to study withdrawal and MAEs will be prepared.

	
From birth to 6 months after birth (Visit 4-NB), occurrences of RSV-associated LRTI(s), Severe LRTI(s), very severe LRTIs and RSV-associated hospitalizations (according to the case definitions in Section 4.2.6 in the protocol)
	
For each category:
 
 - RSV-associated LRTI, - Severe LRTI, - Very severe LRTI - RSV-associated hospitalization 
The number and proportion (with 95% CI) of subjects with at least one event will be calculated and tabulated by group.

CONFIDENTIAL209544 (RSV MAT-004)
Statistical Analysis Plan Amendment 3**5.3.2. Additional considerations****5.3.2.1. Analysis of solicited events**

The analysis of solicited events will be performed on Solicited Safety Set. The intensity of the following solicited events will be assessed as described:

Table 7 Intensity scales for solicited symptoms in adults

Adults/Child (≥6 years)		
Adverse Event	Intensity grade	Parameter
Pain at injection site	0	None
	1	Mild: Any pain neither interfering with nor preventing normal every day activities.
	2	Moderate: Painful when limb is moved and interferes with every day activities.
	3	Severe: Significant pain at rest. Prevents normal every day activities.
Redness at injection site		Record greatest surface diameter in mm
Swelling at injection site		Record greatest surface diameter in mm
Temperature		Record temperature in °C/°F (with 1 decimal) Temperature will be analysed in 0.5°C increments from ≥ 38.0°C /100.4°F) Grade 3 fever is defined as > 39.0°C /102.2°F
Headache		
Fatigue	0	Normal
Nausea	1	Mild: Easily tolerated
Vomiting	2	Moderate: Interferes with normal activity
Diarrhea	3	Severe: Prevents normal activity
Abdominal pain		

The maximum intensity of solicited administration site redness/swelling will be scored at GSK Biological as follows:

0	:	≤ 20 mm
1	:	> 20 mm to ≤ 50 mm
2	:	> 50 mm to ≤ 100 mm
3	:	> 100 mm

Duration in days of solicited administration site and systemic events within 7 days after vaccination will be tabulated by study group and overall, and if needed by age group. The derivation rule of duration in days for solicited events is detailed in section [10.1.3.9](#)

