5.2.2.3. Between group analysis

This analysis is exploratory.

For the analysis of maternal subjects at each time point (Day 31, Delivery, and Day 43 post-delivery), the model will be explored and fitted via the proc mixed procedure according to the following code:

```
PROC MIXED data=sero;
  CLASS /*subjid*/ group ges_age_cat age_cat center;
  MODEL log_val = baseline group ges_age_cat age_cat
inter_vac_del center /ddfm=kenwardroger outp = pred;
  /*RANDOM Subjid*/;
  LSMEANS group/pdiff cl alpha=0.05;
RUN;
```

where log_val represents the log-transformed antibody value of the immunogenicity variable at a given post baseline timepoint, group indicates the study group, ges_age_cat is the gestational age category at vaccination ($28^{0/7}$ - $31^{0/7}$, $31^{1/7}$ - $33^{6/7}$ weeks), age_cat is the age category at vaccination (18 – <35 years and \geq 35 years), inter_vac_del is the interval between vaccination and delivery (days). The inclusion of age category at vaccination, interval between vaccination and delivery, and center in the model depends on the availability of the variable (inter_val_del may not be available at Day 31 analysis) and the necessity, therefore, the above SAS code serves as a reference and may be adjusted according to the analysis needs.

CONFIDENTIAL209544 (RSV MAT-004)
Statistical Analysis Plan Amendment 3

For the analysis of infants at each time point (cord blood at Delivery, Day 43 post-birth, Day 121 post-birth, and Day 181 post-birth), similar model will be explored:

```
PROC MIXED data=sero;
  CLASS /*subjid*/ group center ges_age_cat ges_age_birth;
  MODEL log_val = baseline group ges_age_cat /*inter_vac_del*/
  ges_age_birth center /ddfm=kenwardroger outp = pred;
  /*RANDOM Subjid*/;
  LSMEANS group/pdiff cl alpha=0.05;
  RUN;
```

Baseline is pre-vaccination logarithm10 transformation of the concentrations/titers from maternal subjects, ges_age_birth is gestational age category at birth (> 37 weeks; ≤ 37 weeks) for infants. With the inclusion of gestational age category at vaccination (ges_age_cat) in the model, this categorical variable ges_age_birth provides similar information as continuous variable inter_vac_del, therefore the inclusion of either variable in the model could be adjusted according to the analysis needs.

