The ratio of GMTs/GMCs between vaccine groups and the corresponding 95% CI will then be constructed by exponentiating the mean difference and its confidence interval between vaccine groups on the logarithm10 scale estimated from the model. Summary tables will show adjusted GMT/GMC for vaccine groups, and ratios of GMTs/GMCs between vaccine groups along with the 95% CI.

If deemed necessary, an analysis of variance model for repeated measures will be fitted to assess the mean profile in each group over time for both maternal and infant subjects separately. Below is the sample SAS code for the analysis of maternal subjects, and similar codes could be explored for the analysis of infants.

```
PROC MIXED data=sero;
  CLASS subjid group visit age_cat center ges_age_cat;
  MODEL log_val = baseline group | visit age_cat ges_age_cat
  inter_vac_del center/ddfm=kenwardroger outp = pred;
  RANDOM subjid;
  /*REPEATED visit/subject=subjid(group) type=un;*/
  LSMEANS group*visit/pdiff cl alpha=0.05;
  RUN;
```

Summary tables will present adjusted GMT/GMC with 95% CI for each group at each timepoint.

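### The exploratory ROC comparison of the two doses starts on an undefined condition and reports bare percentages with no interval, so chance gaps between doses will often look like separation

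*SAP*

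**What the plan says.** Section 5.2.2.5 of the current SAP (Amendment 3) introduces the ROC work as follows: "This analysis is exploratory and complementary to traditional data analysis methods". It gives two conditions for running it. One is discretionary: the analysis "will be performed on the PPS only if deemed necessary". The other depends on a result: "If immune response between active vaccination groups can't be differentiated using traditional approach, additional analyses using a generalized ROC" method will be performed. No p-value, interval rule, assay or timepoint defines when the doses count as not differentiated.

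The scope is "for both RSV-A neutralizing antibody titers and RSVPreF3 IgG specific antibody concentrations at Day 31 and Delivery", with other timepoints if needed. There are two variants. In ROC-P, the post-vaccination levels of both doses "will be pooled and used as a reference distribution". In ROC-B, the reference is the pre-vaccination levels of both dose groups.

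The outputs are a figure and a table: "A summary table will be provided on the thresholds of e.g. 25%, 50% and 75% percentiles of the reference distribution", with the percentage of each dose group at or above each threshold. No interval, area or test is requested.

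The between-group model in section 5.2.2.3 reports "ratios of GMTs/GMCs between vaccine groups along with the 95% CI", with the level set by "LSMEANS group/pdiff cl alpha=0.05". Section 5.2.1 also asks for an exact 95% CI on the percentage of infants with placental transfer of at least 1.

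**The concern.** There are two weaknesses.

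**The start rule.** The ROC is called for when the model leaves the doses unseparated and is not required when the model separates them. A change of verdict prompted by the ROC can therefore run from not differentiated to different, and nothing plans for the reverse. Since the condition is undefined, two analysts with the same model output could disagree on whether the ROC is due.

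**The output.** A table of percentages for two groups of 70 to 100 women, over two assays, two timepoints and about three thresholds, will contain visible gaps even if the doses are identical. Without an interval the reader cannot tell these from a real difference. The percentages also lack the baseline and gestational-age adjustment of the model.

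What is at stake is the descriptive reading of how 60 and 120 compare, in the one section headed as dose characterisation.

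**Working it through.** The SAP gives no sample size, error rate or gap threshold for this analysis, so there is no planned figure to reproduce.

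**Inputs from the SAP**
- 213 women were vaccinated (SAP Amendment 2, section 1), allocated 1:1:1. 213 / 3 = 71 per group, assuming an equal split and no per-protocol losses.
- The planned ceiling is 100 per group (section 3, Table 2).
- 2 assays × 2 timepoints × 3 percentiles = 12 ROC-P cells.
- The model level is two-sided 0.05.

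**Step 1: noise at one threshold.** This step depends on group size alone. With identical doses and a pooled median threshold, the number x of one group's n women in the upper half of 2n is hypergeometric. Its variance is n × ¼ × n/(2n−1), and the gap is (2x − n)/n.
- n = 71: variance 71 × 0.25 × 71/141 = 8.94, SD of x 2.99, SD of the gap 2 × 2.99/71 = 8.4 points. A 95% interval for the gap is about ±16.5 points. P(gap ≥ 10 points) = 0.18.
- n = 100: variance 100 × 0.25 × 100/199 = 12.56, SD of x 3.54, SD of the gap 7.1 points. The interval is about ±13.9 points. P(gap ≥ 10 points) = 0.20.

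The Clopper-Pearson interval for a single percentage near 50% is 38.6 to 62.8% (36/71) or 39.8 to 60.2% (50/100).

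**Step 2: all 12 cells, given that the model separates nothing.** This used 4,000 simulated trials per setting with no dose difference. The following are assumptions that the SAP does not give: log10 SD 0.35; correlations of 0.5 to 0.6 between baseline and post-vaccination, 0.5 to 0.7 between assays and 0.7 to 0.8 between timepoints; and not differentiated taken as p > 0.05 in all four comparisons. That condition was met in 84 to 87% of trials.

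| | 71 per group | 100 per group |
|---|---|---|
| At least one ROC-P gap ≥ 10 points, undifferentiated trials | 75–78% | 64–75% |
| At least one ROC-P gap ≥ 15 points, undifferentiated trials | about 30% | 8–13% |
| At least one ROC-P gap ≥ 10 points, ROC always run | 79–81% | 74–78% |

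The width of the first range at 100 per group comes mainly from whether gaps of exactly 10 points are counted: 64–67% if some are lost to rounding, 70–75% if all are counted. Exact 10-point gaps cannot occur with 71 per group.

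**Step 3: what the trigger contributes.** Compare the first and third rows. Running the ROC only after a non-difference does not raise the chance of a spurious gap; it lowers it slightly.

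**Step 4: ROC-B.** In undifferentiated trials with no dose difference and a 4-fold rise, a gap of 10 points or more appeared in 20% (n = 71) or 11% (n = 100). At a 10-fold rise it appeared in none, because both curves sit near 100%. With a true ratio of 1.25 and a 10-fold rise there was still none.

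**Step 5: a single area instead.** With no difference, the SE of the Mann-Whitney area is √[(2n + 1)/(12n²)]. For n = 71 this is √(143/60,492) = 0.049, or about ±0.095 around 0.5. For n = 100 it is √(201/120,000) = 0.041, or about ±0.080. In undifferentiated trials with 71 per group, the Mann-Whitney test reached p < 0.05 in at least one of the four cells in about 3 to 4% when the first comparison was an unadjusted two-group test, and in about 8% when it was baseline-adjusted. The comparable figure for bare 10-point gaps is 75 to 78%.

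**The case against.** The strongest reply is that nothing hangs on this display. It is labelled exploratory and complementary, section 6 makes all comparative analyses descriptive and asks for caution, and no dose-selection rule uses the ROC. The adjusted ratio and its 95% CI are in hand whenever the ROC is run. The 10-point mark is a reviewer's choice, and the largest of 12 correlated cells is an unkind summary: a gap of that size in one direction at all three percentiles of an assay and timepoint occurred in only about 2 to 5% of undifferentiated trials at 71 per group. Allocation was minimised on gestational age, maternal age and center, so the missing adjustment matters little. The tables are laid out in a separate document that is not shown, so the absence of an interval is established only for the SAP text. All of this stands, and it limits the weight of the point. The exploratory label does not rank the ROC below the model, however, since section 5.2.2.3 calls the model exploratory too.

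A reader might infer that the ROC can only push the reading toward a dose difference. The SAP does not support that. An undifferentiated result is inconclusive, and overlapping curves can move it toward the doses being alike. All 12 ROC-P gaps stayed below 10 points in roughly a quarter of undifferentiated trials at 71 per group, and a saturated ROC-B can suggest similarity even when the doses differ.

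A reader might also blame the conditional trigger for the chance separations, or count ROC-B as many further looks. Steps 3 and 4 do not bear out either reading.

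**Conclusion.** The point holds in a limited form. The start condition is undefined and depends on the result, so the ROC can overturn a non-difference and need not be set against a difference already found. The table has no interval, although the sampling error on a between-dose gap near the median is about ±14 to 16.5 points. With identical doses and 71 per group, about three in four undifferentiated trials would show some ROC-P gap of 10 points or more, and about three in ten a gap of 15 or more. The cause is noise read across 12 cells without intervals.

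The single-threshold figures rest only on group size. The 12-cell figures also rest on the assumed correlations and on the assumed meaning of not differentiated. Severity is minor: the analysis is exploratory, has no decision rule and sits beside an adjusted ratio with its CI.

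**What to change.** In section 5.2.2.5:

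1. Delete both conditions, the one on necessity and the one on the doses not being differentiated. Run the ROC for RSV-A neutralising titres and RSVPreF3 IgG at Day 31 and Delivery whatever the GMT/GMC ratio shows.
2. Report one 120-versus-60 area (Mann-Whitney probability) with a 95% CI for each assay and timepoint, beside the adjusted ratio.
3. Keep the percentile table, and add a 95% CI for the between-dose difference at each threshold.
4. State that the ROC does not override the adjusted GMT/GMC ratio.

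Item 1 removes the asymmetry and the ambiguity. Items 2 and 3 deal with the chance gaps, which item 1 alone would not reduce. Four areas are still four looks: with identical doses and the ROC always run, a Mann-Whitney test reaches p < 0.05 in at least one of them in about 14 to 16% of trials at 71 per group, so the caution in section 6 should stay.

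The cost is SAP wording, a little programming and a display that looks less decisive. No new data are needed.
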